## A. Background

Asthma symptom control is suboptimal in the majority of children in the United States, despite widespread availability of asthma controller medications and standardized treatment guidelines. While deaths from asthma have declined, 53.7% of children with asthma continue to experience an exacerbation each year and the associated public health burden is substantial. Indeed, national surveillance data in children highlight disturbing trends of decreased primary care visits for asthma, increased emergency department visits for asthma exacerbations, and rising asthma costs estimated at \$82 billion annually. School absenteeism and decreased productivity in working parents are also consequences of childhood asthma that negatively impact affected children and their families.

While the factors responsible for poor asthma symptom control are complex and include limited access to care, poor adherence to preventative asthma medications and exposures to environmental allergens and irritants such as tobacco smoke, it is also recognized that children with exacerbation-prone asthma are a heterogeneous group with differing clinical outcomes and longitudinal disease trajectories.

** Symptoms (defined as subjective sensations)** can also be quite varied within and among affected children. Whereas some children have persistent, troublesome respiratory symptoms, others have respiratory

**Figure 1.** Symptom domains (large circles) and potential symptom clustering (overlap areas) in children with exacerbation-prone asthma.

symptoms only with upper respiratory infections. Mental health symptoms and social health symptoms have been inadequately characterized in this population, but some children with asthma also report depression and anxiety and impaired family functioning and relationships that may further worsen asthma outcomes. However, prior studies are limited by a narrow focus on individual symptoms in isolation. To date, there has been no attempt to identify **symptom clusters (defined as two or more concurrent symptoms independent of other clusters) (Figure 1)** in children with exacerbation-prone asthma.

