### **Aim 1. Identify and phenotype symptom clusters and assess their temporal trajectories in children with exacerbation-prone asthma.**

Hypotheses: A cluster of children with the poorest physical, mental, and social health symptoms will be identified by latent class analysis; this cluster will have stable symptom presentations over time.

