### **Aim 3. Identify inflammatory and metabolic pathways underlying symptom clusters in children with exacerbation-prone asthma.**

Hypotheses: Symptom clusters will be distinguished by systemic and airway inflammatory cytokine profiles and metabolomic biomarkers.

[name] is also receiving supplemental funding to pursue two additional aims related to climate change. Climate change poses a significant threat to respiratory health in patients with asthma. The effects are direct, through extreme heat or humidity, and indirect, through

synergistic disturbances in air quality and airborne allergens. For example, rising temperatures accelerate production of pollutants such as ozone, fine particulate matter (PM2.5), polycyclic aromatic hydrocarbons, and volatile compounds, which alter airway function and host defense through epigenetic modifications in immune cells, airway eosinophil infiltration and epithelial inflammation. Heavy metals, nitrates and sulfur pollutants can also agglomerate on the surface of pollen grains and may increase allergenic potential and absorption of these toxicants once inhaled.

The effects of climate change and air pollution are not equal. **Children are more susceptible.** Children have a higher respiratory rate and minute ventilation, which increases pollutant inhalation, and more narrow airways, which amplify particulate trapping, absorption, and epithelial inflammation and oxidative stress. The negative effects of climate are increased further in **socially vulnerable populations**. Black and Hispanic children are more likely to live in lower opportunity neighborhoods due to systemic structural racism and historic red lining practices, are exposed to more pollutants, and have more severe asthma exacerbations attributable to air pollution. They are also projected to have a 1.3-fold risk of living in a neighborhood with the highest projected increases in asthma due to increased PM concentrations. In these neighborhoods, fears about crime and safety and limited recreational green space also force children indoors. However, poorer housing standards allow for increased infiltration of outdoor pollutants into the home. Impaired ventilation or filtration also results in 2-5 higher pollutant concentrations when compared to what is experienced outdoors.

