## D. Innovation

**Novel concepts.** Whereas other studies have focused on single symptom manifestations (i.e., wheeze or anxiety) in children with exacerbation-prone asthma, this would be the first study to:

- Identify and phenotype **symptom clusters** in children with exacerbation-prone asthma using validated, age-appropriate PROMIS measures and a novel statistical analytical technique in symptom science research, latent transition analysis, to address temporal symptom trajectories,
- Examine whether identified symptom clusters predict objective and patient-reported clinical outcomes (corticosteroid treatment responsiveness and quality of life) that are important to both physicians and affected patients, and
- Link symptom clusters with inflammatory/metabolic pathways that could be targeted with future interventions.

The results of this study could have a significant impact on the assessment and management of children with asthma through identification of high-risk children who might benefit from personalized medicine approaches. While national asthma treatment guidelines do recognize the importance of respiratory symptoms, these guidelines provide no guidance regarding the assessment and management of non-respiratory symptoms in affected children.

To address these critical knowledge gaps, we will perform extensive clinical characterization and state-of-the-art laboratory analyses of children with exacerbation-prone asthma. We will also use an adaptation of the conceptual framework proposed by Brant et al.

that incorporates temporality (**Figure 2**). Our framework proposes that: 1) children with exacerbation-prone asthma and a unique mixture of covariates possess an equally unique set of inflammatory/metabolic pathways that are each associated with symptoms, 2) those symptoms synergize positively or negatively in a symptom cluster that may or may not evolve over time, and 3) symptom clusters impact asthma outcomes.

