#### **F. Rationale for heterogeneous study population**

In children, asthma symptoms are complex and result from a variety of triggers including allergens, irritants, pollutants, microbes, viruses, psychological stressors and emotions. These triggers induce airway changes such as mucus production, hyperresponsiveness, smooth muscle hypertrophy and constriction that result in respiratory symptoms (and consequent physical, mental and social health symptoms). However, triggers act through different pathways (**Figure 3**) and likely yield different symptom clusters. For example, allergen sensitization is associated with Type-2 (i.e., Th2) eosinophilic inflammation and is thought to be a pivotal risk factor for persistent and severe wheezing and airflow obstruction. By contrast, children with non-Type-2 neutrophilic inflammation tend to wheeze only with respiratory viruses and often have cessation of asthma symptoms during later childhood. Children with non-Type-2 inflammation also have increased IL-8 expression during the course of the exacerbation, which may reflect innate immune impairment in response to viral or bacterial exposures.

[figure not shown]
Nonetheless, the paradigm of “Type-2” versus “non-Type-2” inflammation is not quite as simplistic as depicted and there can be synergy of triggers and pathways. For example, in addition to being a pivotal risk factor for asthma persistence, Type-2 inflammation has also been associated with increased severity of upper and lower respiratory tract infections and a

greater risk of hospitalization for human rhinovirus infection Psychological

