**Spirometry with Oscillometry.** Spirometry for measurement of lung function will be performed with a portable spirometer (MGC Diagnostics® CPFS/D USB™) according to technical standards. The best of three forced vital capacity maneuvers will be interpreted according to population reference standards. Oscillometry will be performed in cooperative participants (typically age 3 and older) with the TremoFlo C-100 device (Thorasys). Participants will wear a noseclip and take tidal breaths through a mouthpiece for 20 seconds. Airway resistance and reactance will be recorded.

**Bronchodilator reversibility testing.** Participants will receive 4 inhalations of albuterol from a metered dose inhaler (MDI) and valved holding chamber and spirometry will be repeated 15 minutes later.

**Exhaled nitric oxide.** Exhaled nitric oxide will be measured with a commercial device (NIOX VERO®, Circassia) using recommended standards. The procedure is non-invasive and considered to be an indirect measurement of airway inflammation. Participants will be instructed to take in a deep breath and blow air out at a constant pressure. One measurement will be taken and recorded.

**Venipuncture.** Blood will be collected by venipuncture as outlined in the table below. Participants will have the option to receive anesthetic cream prior to venipuncture.

Test	Where performed	Test code	Visits	Collection tube	Blood collection volume
Total IgE and Specific IgE	Children's	TIGE, INHALA Panel	1	Gold top SST	1.5 mL
Complete blood count with differential	Children's	CBED	1,2,5	Lavender EDTA	1 mL
Cytokines, metabolomics	[name] lab		1,2,5	Lavender EDTA Blue tempus	~6 mL ~3 mL (+6 mL solution)

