Because LTA is aimed at characterizing transition over time, it requires variability in all variables. Therefore, we will perform LTA with patient-reported symptoms (global, mental, social and physical health categories) and measures of asthma disease activity (ACQ, ACT, lung function, exhaled nitric oxide, blood eosinophils) measured at baseline and visits 3, 4 and 5 (**see Appendix 1**). Age, sex, race, ethnicity, socioeconomic status, medications, exposures and allergic sensitization measured at the baseline visit will be considered stable and treated as covariates in the LTA model. All participants will be included in the analysis since missing data for the variables are handled in the procedure, with data assumed to be missing completely at random. The test of the null hypothesis that data are missing completely at random (Missing Completely At Random test in the SAS LTA procedure) will be evaluated; if non-significant, missingness does not affect the interpretation of the results. The number of classes will be statistically determined using the Bayesian information criterion (**BIC**) and class prevalence if BICs are of a similar magnitude, to avoid a solution leading to low prevalent groups (<5%). To assess the stability of the group structure, goodness of fit of the “constrained” LTA model in which identical item-response probabilities across time are estimated (i.e., the same cluster structure is forced into multiple time points) will be compared with the “unconstrained” LTA model in which item response probabilities are estimated at each time point. To further address sex as a biological variable, models will also be fitted by sex, with statistical comparison of results observed in boys and girls. All analyses will be performed with SAS software version 9.4 (SAS Institute) using the PROC LTA procedure.

The primary outcome will be assessed after assignment of individuals to the latent classes that they had the highest probability of belonging to (based on the posterior probability provided by the model at baseline). A straightforward analysis of the primary outcome will follow and involves comparison of the proportion of children achieving a minimally importance difference in ACQ of at least 0.5 in each of the latent classes via a Chi-Square test.

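### The symptom clusters are built partly from FeNO, blood eosinophils and lung function, so Aim 3 can find inflammatory differences between clusters even when symptoms are unrelated to inflammation

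*Combined protocol and SAP*

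**What the plan says.** Section U (plan for aims 1-3) names two groups of variables that define the latent classes. The first is given as "we will perform LTA with patient-reported symptoms (global, mental, social and physical health categories". The second is "measures of asthma disease activity (ACQ, ACT, lung function, exhaled nitric oxide, blood eosinophils) measured at baseline and visits 3, 4 and 5". Age, sex, allergic sensitization and similar baseline variables are listed separately as covariates, so the disease-activity measures are class-defining indicators.

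Elsewhere the protocol describes the clusters by symptoms. Section A has "Symptoms (defined as subjective sensations" and defines a symptom cluster as at least two symptoms occurring together. Aim 1 expects that "A cluster of children with the poorest physical, mental, and social health symptoms will be identified by latent class analysis". Section D says the clusters will be identified "using validated, age-appropriate PROMIS measures".

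The protocol also treats two of the added indicators as inflammation. Section L says FeNO is "considered to be an indirect measurement of airway inflammation", and Section F says that "allergen sensitization is associated with Type-2 (i.e., Th2) eosinophilic inflammation".

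The Aim 3 hypothesis is "Symptom clusters will be distinguished by systemic and airway inflammatory cytokine profiles and metabolomic biomarkers". Section U tests it with linear mixed models relating cytokine, metabolomic and amino acid data to cluster assignment. Secondary analyses use 0.05 without multiplicity adjustment, and no separate threshold is given for Aim 3. No LTA restricted to symptoms is planned, even as a sensitivity analysis.

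**The concern.** Aim 3 is the mechanistic part of the study. Section G expects inflammation to be greatest in the cluster with the poorest symptoms and attributes it to symptoms acting together. That inference requires clusters formed without reference to inflammation. Here children may be sorted partly on FeNO and eosinophils and then compared on cytokines from the same pathway. A positive result could mean only that children grouped by Type-2 markers differ in other Type-2 markers, and the planned analysis could not tell the two explanations apart.

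The indicator set also affects what the classes mean in Aims 1 and 2. They would be classes of symptoms plus disease activity, which is not how Section A defines a symptom cluster.

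**Working it through.** **The plan's own figure.** The documents state no power or error rate for Aim 3. The nearest figure is Table 3, for the primary chi-square test. With N=147, df=3 and W=0.275, the noncentrality is N × W² = 147 × 0.075625 = 11.12. The chance that a noncentral chi-square exceeds the 5% critical value is then 0.808, as printed. All 45 cells reproduce (largest difference 0.0014), and 173 × 0.85 = 147. Table 3 does not depend on the point made here.

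**Simulation for Aim 3.** From the documents: N (173 enrolled or 147 final), four classes (Section T), BIC choice of classes (Section U), alpha 0.05, and the indicator list. Assumed, because the documents do not give them: all loadings and correlations, binary indicators, and a single symptom trait. Symptoms were generated independently of a Type-2 trait that drives FeNO, eosinophils and, more weakly, lung function. A baseline latent class model was fitted, each child was assigned to the most probable class, and one marker was compared across classes by a one-way F-test. Any rejection rate well above 5% is then an artefact of the indicators.

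The number of symptom indicators is open. Section U can be read as four category scores plus ACQ and ACT (4 + 2 = 6) or as the 13 PROMIS forms of Section L plus ACQ and ACT (13 + 2 = 15).

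*Series A*: N=173, 400 runs, four classes, FeNO and eosinophil loading 0.70. Here r is the marker's correlation with FeNO and eosinophils.

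| r | 6 indicators: planned / symptom-only | 15 indicators: planned / symptom-only |
|---|---|---|
| 0 | 4.8% / 5.5% | 3.5% / 5.5% |
| 0.2 | 33% / 6.0% | 12% / 5.5% |
| 0.3 | 62% / 5.5% | 28% / 7.2% |
| 0.4 | 87% / 5.8% | 39% / 7.2% |

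*Series B*: N=147, 6 symptom indicators, lung function loading 0.4 on each trait, four classes, 80 runs. Here the correlation is with the Type-2 trait itself. (On that scale, r=0.4 in Series A is 0.4/0.70 = 0.57.)

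| FeNO/eosinophil loading | Correlation | Planned | Symptom-only |
|---|---|---|---|
| 0.70 | 0.4 | 45% | 8% |
| 0.70 | 0.6 | 84% | 9% |
| 0.85 | 0.4 | 81% | 5% |
| 0.85 | 0.6 | 99% | 8% |

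Repeats gave 49% to 53%, 81% and 77% for the first three rows. With 15 symptom indicators (loading 0.70, correlation 0.4) the planned set gave 23%.

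**With the number of classes chosen by BIC, as planned.**

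| Symptom indicators | FeNO/eosinophil loading | Planned set |
|---|---|---|
| 6 | 0.70 | 8% to 13% |
| 15 | 0.70 | 4% to 7% |
| 15 | 0.85 | 5% to 11% |
| 6 | 0.85 | 34% to 47% |

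These ranges pool Series A at r=0.3 (200 runs) and the Series B setup at 0.4 and 0.6 (40 to 150 runs where recorded). Symptom-only classes in Series A gave 5% to 8%. BIC usually kept two or three classes. In Series A with 6 indicators, the mean number under the planned set rose from 2.02 at loading 0.70 to 2.47 at 0.85, which is where the inflation appeared.

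Monte Carlo error, √(p(1−p)/n), is about 1 point at 5% with 400 runs, 4 points at 47% with 150 runs and 8 points at 43% with 40 runs.

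**The case against.** The strongest reply is that four classes is only a sample-size assumption, while the analysis rule is BIC followed by class prevalence. Under that rule most settings gave rates close to nominal, because the retained classes were driven by symptoms. This stands, and it is why the four-class figures cannot serve as the expected error rate. It does not remove the problem: the sponsor cannot know in advance whether a class will separate on the biomarkers, and one plausible setting gave 34% to 47%. The simulations also assume one symptom trait; a richer structure could retain more classes.

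Second, the Aim 3 outcomes are cytokines and metabolites, not FeNO or eosinophils. Many markers on a broad panel, such as the non-Type-2 IL-8 of Section F, need not track eosinophils, and at zero correlation nothing is inflated. This also stands. A reader might infer that the clusters must differ on inflammation by construction. The documents do not support that; the effect needs both a class that separates on the biomarkers and a marker correlated with them.

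Third, Section D says PROMIS measures are used, not that they are used alone; Section U openly labels the added variables as disease activity; and item-response probabilities would show a class that separates on FeNO or eosinophils. That helps a reader detect the problem, but without a symptom-only model there is nothing to put in its place.

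Finally, eosinophils are scheduled only at visits 1, 2 and 5, and FeNO and spirometry are skipped at telephone visits, so these indicators are sparse during follow-up. They are scheduled for everyone at baseline, where classes are assigned for the primary outcome. The plan does not say which assignment Aim 3 uses.

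**Conclusion.** The overlap is in the plan's text, and a positive Aim 3 result could not be attributed to symptoms as the analysis stands. Its size is uncertain. With symptoms independent of inflammation, the chance of a significant result for one marker was about 12% to 99% with four classes and assumed correlations of 0.2 to 0.6. Under the planned BIC rule it was about 4% to 13% in most settings and about 34% to 47% with strongly related FeNO and eosinophils and few symptom indicators. Symptom-only classes gave about 5% to 9%. All loadings and correlations are assumptions.

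A reader might also infer that the primary analysis is undermined. Nothing here shows that: Table 3 is unaffected, no error rate for the primary test was derived, and Aim 3 is neither the primary nor the secondary outcome. For Aims 1 and 2 the point concerns what the classes are called and mean. This should be fixed before the Aim 3 analysis, but it is not a flaw in the trial as a whole.

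**What to change.** In Section U:

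- Prespecify an LTA on patient-reported measures only: the PROMIS domains, ACT or C-ACT, and the ACQ without its lung-function item. Section L says the 7-item ACQ includes lung function, so the full score would bring that indicator back. State how many symptom indicators enter and how they are categorised.
- Make this model's class assignment the sole basis for Aim 3 inference, and say which visit's assignment is used.
- Compare FeNO, eosinophils and lung function across the finished classes as external variables.
- The mixed-indicator model may stay for Aims 1 and 2. If so, label its classes as symptom-plus-disease-activity classes, report whether the Aim 1 and 2 results hold with symptom-only classes, and draw no Aim 3 inference from it.

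The cost is a second LTA and the associated text; no new data are needed. The downside is that symptom-only classes may be fewer or less well separated.

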**Follow-up visits (Visits 3 and 4), Study Week 16, 32 (window +4 weeks)**

1. Brief physical examination (by RN) including height and weight performed\*
2. Medical history obtained
3. Urine pregnancy testing\*
4. Asthma control evaluation (Asthma Control Questionnaire and Asthma Control Test)
5. Administer PROMIS symptom questionnaires
6. Measure exhaled nitric oxide\*
7. Perform spirometry with oscillometry\*

\*procedure will not be performed if follow-up occurs by telephone

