**Final follow-up visit (Visit 5), Study Week 48 (window +4 weeks)**

1. Brief physical examination (by RN) including height and weight performed\*
2. Medical history obtained
3. Urine pregnancy testing\*
4. Asthma control evaluation (Asthma Control Questionnaire and Asthma Control Test)
5. Administer PROMIS symptom questionnaires

6. Measure exhaled nitric oxide\*
7. Perform spirometry with oscillometry (with bronchodilator reversibility)\*
8. Perform venipuncture:
  - a. Complete blood count with differential (Children's Healthcare of Atlanta)
  - b. Plasma and white blood cells for aim 3 ([name] laboratory)
9. Perform sputum induction with samples stored for aim 3 ([name] laboratory)\*

\*procedure will not be performed in follow-up occurs by telephone

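### The latent transition analysis uses blood eosinophils at two visits with no blood count, and lets a non-significant MCAR test close the missing-data question

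*Combined protocol and SAP*

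**What the plan says.** Section U (plan for aims 1-3) fits the LTA with patient-reported symptoms and "measures of asthma disease activity (ACQ, ACT, lung function, exhaled nitric oxide, blood eosinophils) measured at baseline and visits 3, 4 and 5", and points the reader to the appendix schedule. Stability of the group structure is judged by comparing a model that forces the same response probabilities at every occasion with an unconstrained "LTA model in which item response probabilities are estimated at each time point".

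On missing data, the same section keeps every participant in the analysis, "with data assumed to be missing completely at random", and plans a test of that assumption: "if non-significant, missingness does not affect the interpretation of the results". It gives no step for a significant result and no sensitivity analysis.

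Section L states: "Blood will be collected by venipuncture as outlined in the table below". That table (Table 2) gives the complete blood count at visits 1, 2 and 5. Section K lists no blood draw at visits 3 and 4. It stars the examination, pregnancy test, nitric oxide and spirometry there, with the note "procedure will not be performed if follow-up occurs by telephone". Section E lets families choose Option 1 (one visit, then remote contacts) or Option 2 (five visits). Within Option 2 they may choose telephone for visits 3 to 5.

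**The concern.** There are two separate problems in one paragraph of the plan.

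First, the LTA is specified on data the trial does not collect. An estimate for eosinophils at visits 3 and 4 needs at least some children with a value there, and none is scheduled to have one. The analyst would have to decide what to do about this after the data are in.

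Second, the plan turns failure to reject MCAR into a conclusion that missing data do no harm. What is at stake is the Aim 1 result on transitions and stability. After baseline, its lung-function and nitric oxide information comes only from children seen in person, and one non-significant p-value would end any inquiry into that.

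**Working it through.** **Eosinophils: indicator list against schedule**

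| LTA occasion | Section U lists eosinophils | Section K visit list | Table 2 (section L) | Appendix I |
|---|---|---|---|---|
| Baseline (visit 1) | yes | blood count | yes | X |
| Visit 3 | yes | none | no | blank |
| Visit 4 | yes | none | no | blank |
| Visit 5 | yes | blood count | yes | (X): not done by telephone |

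Three places in the schedule agree with each other and disagree with section U, so this is not an artefact of a broken table.

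The plan gives no missingness figure of its own to reproduce. Its attrition figure does check: 173 × (1 − 0.15) = 147.05, stated as 147 in section T.

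- Child-occasions: 173 × 4 = 692.
- Most that can have a scheduled count: 173 × 2 = 346.
- Absent by design: 692 − 346 = 346, or 50%. This is a lower bound. It takes every child as Option 2, in person, with no dropout.
- With the plan's attrition reached by visit 5 and everyone left seen in person: 692 − 173 − 147 = 372, or 54%.

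The documents give no uptake of Option 1 or of telephone visits. As an assumption, let a share u of children have no in-person visits 3 to 5, before dropout and on the Appendix I reading of visit 5 blood:

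- Eosinophils absent: 1 − (1 + (1 − u))/4 = 56% at u = 0.25 and 62.5% at u = 0.50.
- Spirometry and nitric oxide absent: 1 − (1 + 3(1 − u))/4 = 19% and 37.5%.

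**Why the item cannot be estimated there.** In the LTA likelihood each child contributes response probabilities only for items observed at that occasion. If no child has an eosinophil value at visit 3, the visit 3 eosinophil probabilities appear nowhere in the likelihood and any value fits equally well. A procedure that tolerates missing values does not change this. The unconstrained model gains nothing in fit from those parameters, so comparing it with the constrained model says nothing about the item at visits 3 and 4. Baseline against visit 5 can still be compared.

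**The MCAR rule: what is missing follows the family's choice**

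| Route chosen | PROMIS, ACT, ACQ at visits 3-5 | Spirometry, nitric oxide at visits 3-5 |
|---|---|---|
| Option 2, in person | scheduled | scheduled |
| Option 2, telephone | scheduled | not done |
| Option 1 | no visits 3-5; ACQ, ACT and asthma impact at week 24 and 48 contacts | none |

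The reasoning then needs no figures:

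1. A non-significant test is failure to reject. It does not establish the null.
2. A test on observed data cannot exclude dependence on values that were not observed.
3. The design gives no reason to expect MCAR, because families select the route that determines which indicators exist.
4. The rule covers one outcome of the test only. A significant result leads nowhere in the plan.

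**The case against.** The strongest reply is that the first part is a drafting conflict. Section U refers to the appendix schedule, which shows the blanks. Eosinophils are one of five disease-activity measures beside 13 PROMIS short forms. PROMIS, ACQ and ACT stay scheduled at Option 2 visits 3 to 5 even by telephone. All of this stands, and it limits the loss to one item at two occasions. It does not remove the conflict, since section U states both the visits and a model that estimates at each of them.

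Several stronger readings are tempting, and the documents do not support them:

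- *The primary result is compromised.* Class for the primary comparison comes from the baseline posterior, and baseline eosinophils are scheduled. Because the model is fitted jointly across occasions there is an indirect effect, which the documents do not allow one to size.
- *The eosinophil gap is itself a breach of MCAR.* It is absent for every child by design. The problem there is identification.
- *Choice of route proves bias.* It makes MCAR doubtful and no more.
- *The MCAR test will usually miss a departure.* A power figure would need the test's degrees of freedom and the size of the departure, and neither is given. The logical point does not depend on one.
- *The plan breaks its own remark that LTA variables must vary.* That sentence explains why changing measures are indicators and stable traits are covariates. It does not concern unmeasured visits.

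**Conclusion.** Both parts hold and should be corrected before analysis. The plan lists an indicator at two of four LTA occasions where it is not collected, so at least 50% of eosinophil child-occasions are absent (54% with the plan's own attrition all falling by visit 5). The stability comparison cannot be made for that item at visits 3 and 4. The rule that a non-significant MCAR test settles the matter is invalid, and the plan is silent on a significant one.

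The consequence is mainly for Aim 1. The 50% rests only on the schedule and N = 173. The percentages above 54%, and those for spirometry and nitric oxide, rest on assumed uptake of Option 1 and telephone visits.

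A further mismatch is editorial: section K does not star the visit 5 blood draw for telephone visits, while Appendix I marks it (X).

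**What to change.** **(a) Reconcile the indicator list with the schedule.** Do not estimate visit-specific eosinophil probabilities at visits 3 and 4. There are two ways:

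- Restrict the item at those two visits only, in both models, and leave baseline and visit 5 free in the unconstrained model. This keeps the one comparison over time that the data can support. The statistician should confirm that the planned software accepts a restriction on one item at chosen occasions.
- Take eosinophils out of the time-varying indicators and use the visit 1 value as a covariate or class descriptor. The downside is that this changes what defines the classes, including the baseline classes used for the primary outcome, and drops the visit 5 value.

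**(b) Replace the missing-data rule.** Delete the sentence that makes a non-significant test decisive. State that data are assumed missing at random given the modelled variables. Report the MCAR test as descriptive only, whatever its result. This leaves the main estimates unchanged.

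**Optional.** Refit the transition and stability results once without spirometry and nitric oxide, and once limited to Option 2 participants. These show how far the results depend on visit mode and on Option 1 children. They do not test dependence on unobserved values.

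**Editorial.** Align the visit 5 telephone marking in section K with Appendix I.

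The cost is SAP wording and, if the optional part is taken up, two extra model fits. No new data are needed.
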